9.2 Sample Size and Study Duration

9.2.1 Stratum 1 NGGCT

In ACNS0122, COG institutions enrolled 79 eligible patients with localized disease over a period of 53 months. Of these 79 patients, 49 (95% lower confidence bound = 53%) would have been eligible based on response to induction therapy to address the primary study objective of this trial for an expected accrual rate of approximately 11.1 patients per year. Thus, we expect that approximately 7 years will be required to accrue the required 77 eligible patients evaluable for the primary objective.

9.2.2 Stratum 2 Germinoma

Based on the publication by Keene et al, the 95% confidence interval estimate of the incidence of CNS germinoma in children 4 to <18 years of age is (0.48, 0.91).⁶⁷ We assume that this estimate holds for 5 to 19 year olds. Canada and US population estimates for 5 to 19 year olds are 6.02 and 61.7 million, respectively. Thus, annually we estimate that there are 32.5 to 61.6 diagnoses of CNS germinomas in patients 5 to 19 years of age. Again based on Keene et al, approximately 77% of patients with CNS germinomas will be diagnosed with localized disease and approximately 75% will present with serum and CSF $\text{hCG}\beta \leq 50$ mIU/ml.⁶⁷ Assuming that 80% of eligible patients would consent to enrolling on this study, we estimate that the annual accrual for patients eligible for the primary study objective will be between 15 and 28 patients. Since 64.7% of eligible patients are expected to be evaluable for the primary objective, annual accrual of eligible, evaluable patients will be between 10 and 18 patients.

Due to the excellent accrual rate of germinoma patients within the initial 2.5 years of study opening (accrual of 80 patients within 27 months), we expect that approximately 5 years will be required as originally estimated to accrue the required 79 eligible patients evaluable for the primary objective. Note that assessing whether the accrual rate is adequate should not begin until one year after the protocol has been released to COG institutions for submission to their Institutional Review Boards (IRB). Receiving IRB approval takes significant time and thus accrual during the first year will no doubt be much less than projected; thus, assessment will begin with the completion of year two.

9.2.3 Total Accrual

Considering 77 eligible, evaluable patients will be required for Stratum 1 and 79 eligible, evaluable patients for Stratum 2, with a 10% ineligible rate, the maximum number of patients expected to be accrued is 275 patients.

As of Amendment #1A, for Stratum 1, the original estimate of the study duration was mistakenly based on the fact that all eligible patients enrolled on Stratum 1 would be evaluable for addressing the primary objective. However, the Stratum 1 primary objective will be addressed only by eligible patients who achieve an objective response and hence qualify to receive reduced radiation therapy. In reality, based on the results from the preceding ACNS0122 study, we had expected that approximately 62% of Stratum 1 eligible patients would experience a CR or PR and would receive reduced radiation therapy. Considering that 77 eligible patients who achieve a CR or PR and receive reduced radiation therapy are required to address the primary objective of Stratum 1, we will need to increase accrual to approximately 125 patients.

For Stratum 2, in order to estimate the study duration, there was no information on which we could estimate the proportion of eligible patients that would experience a complete response or continued complete response and contribute to addressing the primary objective. Seventy-nine (79) eligible, evaluable patients are required to address the primary objective. Currently, based on the ACNS1123 data through 31 December 2013, we estimate that approximately 64.7% of Stratum 2 eligible patients will experience a CR or CCR, receive reduced radiation therapy and contribute to addressing the primary objective. Thus, we need to accrue a total of 123 eligible patients to Stratum 2.

Assuming that the expectation for 62% of Stratum 1 eligible patients and 64.7% of Stratum 2 eligible patients will contribute to addressing the primary objectives is realized, we will need to accrue 248 (125+123) patients and assuming a 10% ineligibility rate, the maximum number of patients expected to be accrued is 275.

9.3 **Methods of Analysis**

9.3.1 Stratum 1 NGGCT

This study will be designed based on the observed outcome for patients treated on ACNS0122. Of 102 eligible patients treated on ACNS0122, 79 (77.5%) were determined to have localized disease. Thirty-two of the 79 (40.5%) patients achieved a CR (N=25) in response to induction therapy or were found on second-

look surgery to have a mature teratoma, residual scar or fibrosis (N= 7). Based on the ACNS0122 data frozen as of June 30, 2011, the 3-year PFS rate for these 32 patients is 90.6% (SE=5.2%) and follow-up was current for all patients. No patient is censored within two years of initiating therapy and 5 patients continue to be followed in their third year. Seventeen of the 79 (21.5%) patients achieved a PR in response to induction therapy and the 3-year PFS rate for these patients is 94.1% (SE=5.7%) with no patient censored within two years of initiating therapy and 2 patients continuing to be followed in their third year. The 3-year EFS point estimate (95% confidence interval estimate) for the 32 CR and 17 PR patients are 90.6% (73.7%, 96.9%) and 94.1% (65.0%, 99.2%), respectively. Thus the 3-year PFS rate for these two cohorts of patients treated on ACNS0122 are both excellent and similar supporting our decision to combine the groups in our study of reduced irradiation. The observed 3-year PFS rate for the combined cohort of 49 patients (32+17) is 91.8% (SE=3.9%).

The historical data from the COG trial ACNS0122 shows that for the 102 patients with localized NGGCT, all failures have occurred within two years of initiating treatment with a single exception of a patient who failed at approximately six years post initiation of treatment. In fact, most failures occurred within one year of initiating treatment. As indicated above, the outcome for the subset of 49 patients treated on ACNS0122 who would have been eligible for treatment on ACNS1123 is exceptional with only three failures in the first year and one in the second year of follow up. Thirty-eight patients have been followed for more than three years. With so few failures in the historical data, the usual time-to-event distributions, exponential, Weibull etc., are difficult to characterize and to assess for adequacy of fit; so the Study Committee has no estimate of a hazard rate and clearly no estimate of median progression-free survival. The binomial distribution appeared to be the best distribution on which to design this trial reflecting the fact that with rare exception all failures are expected to occur early. The binomial distribution parameterized by the 3-year PFS rate is expected to be sufficient to capture virtually all failures and reflects the fact that the investigators are confident that all patients will be successfully followed for at least three years. This method requires that no patient be lost to follow up within the first three years. All patients who fail to be evaluated for progression at the 3-year mark will be included in the primary analysis as failures. The Principal Investigators are committed that no patient be lost to follow up within three years of initiating treatment.

Considering the current results of ACNS0122, a true, unknown 3-year PFS rate of 0.82 for this reduced therapy approach is considered unacceptable by the study team. The sample size calculation will be based on the binomial distribution testing that the true, unknown 3-year PFS rate is at most 82% (null hypothesis: ≤ 0.82) and powered to detect that the 3-year PFS rate is really 93% (0.93). East 5.3[©] was used to calculate the require sample size of 77 patients. This design will reject the null hypothesis if at least 69 patients (≥ 69) are progression free after three years and conclude that reduced therapy is acceptable. Due to the discrete distribution, the actual type I error rate is 0.0492 (probability of falsely concluding that the treatment is effective when the true 3-year PFS rate is 0.82) and statistical power is 0.911 (probability of correctly concluding that the treatment is effective when the true 3-year PFS rate is 0.93).

In order for the reduced therapy approach to be considered to have sufficient merit for continued investigation, our design requires a statistically significant result – p -value < 0.0492. The null hypothesis must be rejected otherwise this approach will have to be reconsidered.

Due to the expected accrual rate, expected low failure rate and three year PFS endpoint, even one interim analysis for futility that would stop accrual early is not feasible. Note that interim analyses would be restricted to patients who are documented failures within three years of initiation of treatment and those patients followed for three years failure free. Thus, no formal futility interim analysis is planned. However, if 9 patients are documented to have failed (progressed or lost to follow up) before three years of follow up and fewer than 77 patients eligible for the primary analysis have begun treatment, accrual will be suspended until the COG Data Safety Monitoring Board (DSMB) has had the opportunity to review all data.

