9.0 STATISTICAL CONSIDERATIONS

9.1 Study Design

The primary objective of the NGGCT stratum 1 is to test whether the subset of NGGCT patients who have a CR or PR in response to induction chemotherapy or who undergo second-look surgery after induction therapy and are found to have only mature teratoma, residual scar or fibrosis can be safely treated with 30.6 Gy WVI and IFR boost up to 54 Gy. The “intent-to-treat” principle will be followed and any eligible patient who receives dose and volume reduced radiation therapy and is evaluable based on response to induction therapy will be included in the primary analysis. The number of patients enrolled in stratum 1 who fail to receive this reduced radiation therapy will also be reported

The primary objective of stratum 2 is to test whether the PFS distribution of localized primary CNS germinoma patients who present with serum and or CSF hCG β \leq 50mIU/ml is sufficient to support continued investigation of the proposed treatment regimen. The “intent-to-treat” principle will be followed and any eligible patient who receives dose-reduced radiation therapy will be included in the primary analysis. The number of patients enrolled in stratum 2 who fail to receive this reduced radiation therapy will also be reported.

In addition, for each stratum descriptive statistics will be provided reporting the proportion of patients who are classified as local, ventricular, distant or a combination of local, ventricular, and/or and distant failures based primarily on imaging evaluation of the neuraxis. See [Section 15.12](#).

The first step in assessing primary objective 1.1.3, modeling neurocognitive function, as assessed on ALTE07C1, will be to monitor the rate of participation of eligible patients treated with dose and volume reduced radiation therapy in stratum 1 and dose-reduced radiation therapy in stratum 2. The same monitoring rule described below will be independently implemented for Stratum 1 and for Stratum 2.

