9.3.2 Stratum 2 Germinoma

The outcome for patients with localized germinoma treated with CSI is even better than the outcome for patients with NGGCT discussed above. Huh, Maity and Bamberg report 10-year PFS of 96.6% (n=32); 5-year PFS of 100% (n=39); and 5-year PFS of 88% (n=49), respectively.³³⁻³⁵ The four relapses in the Bamberg cohort were all within three years of initiating therapy. Calaminus reported an EFS rate of $97 \pm 2\%$ for 128 patients with localized germinoma treated with CSI. Thus, a similar statistical approach is justified for evaluating reduced therapy for patients with localized germinoma. The binomial distribution seems most appropriate for the design for this stratum, as again the usual time-to-event distributions, exponential, Weibull, etc. cannot be well-characterized based on the available data. The 3-year PFS rate was chosen as all failures are expected within three years of initiating therapy and we will successfully follow all patients for at least three years.

Based on the results of the SIOP-96, SFOP trial and Japanese studies, our approach will be considered acceptable if there is statistical evidence that the true, unknown 3-year PFS rate is greater than 0.87 (> 87%). Thus, a one-sided test will be used with a type I error rate of 0.10 ($\alpha = 0.10$) and 90% statistical power ($\beta = 0.10$), if the true 3-year PFS rate is 95%. Since this approach offers the potential for superior quality of life for surviving patients who are spared exposure to highly effective cranial spinal irradiation that has long term consequences for survivors, we have set the statistical power at 90%.

The sample size calculation will be based on the binomial distribution testing that the true, unknown 3-year PFS rate is at most 87% (null hypothesis: ≤ 0.87) and powered to detect that the 3-year PFS rate is really 95% (0.95). This method requires that no patient be lost to follow up within the first three years. All patients who fail to be evaluated for progression at the 3-year mark will be included in the primary analysis as failures. The Principal Investigators are committed that no patient be lost to follow up within three years of initiating treatment. East 5.4[©] was used to calculate the require sample size of 79 patients. This design will reject the null hypothesis if at least 73 patients (≥ 73) are progression free after three years. This approach was selected to minimize the number of patients with this rare

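### The success counts of 69 and 73 fit only 77 and 79 analysed patients, but the analysis set is uncapped and a small overrun is likely

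*Combined protocol and SAP*

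**What the plan says.** Section 9.3.1 tests a 3-year PFS rate of at most 0.82 against 0.93. East "was used to calculate the require sample size of 77 patients", and the rule is: "This design will reject the null hypothesis if at least 69 patients (≥ 69) are progression free after three years". The section adds "Due to the discrete distribution, the actual type I error rate is 0.0492" and that "statistical power is 0.911". It then asks for a significant result, with a p-value below 0.0492.

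Section 9.3.2 tests at most 0.87 against 0.95, one-sided at 0.10 with 90% power and 79 patients: "This design will reject the null hypothesis if at least 73 patients (≥ 73) are progression free after three years". It says that the null must be rejected, but gives no p-value threshold apart from the design level of 0.10.

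Neither section gives a critical count for any other number of patients.

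Section 9.1 defines the Stratum 1 analysis set: "any eligible patient who receives dose and volume reduced radiation therapy and is evaluable based on response to induction therapy will be included". The Stratum 2 definition is similar. Neither stops at the 77th or 79th patient.

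On accrual, Section 9.2.3 expects 62% of eligible Stratum 1 patients to count towards the primary objective, so "we will need to increase accrual to approximately 125 patients". For Stratum 2 it gives 123 eligible patients at 64.7%. In its neurocognitive monitoring text, Section 9.1 says that accrual otherwise runs until the cohort needed for the primary objective has been reached.

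**The concern.** The threshold for success is a fixed number of patients, while the denominator is whatever number of eligible patients goes on to the reduced radiotherapy. Each patient beyond 77 or 79 is another chance to reach the same count, so the rule becomes easier to satisfy as the number grows.

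The number cannot be steered exactly. Whether a patient enters the analysis depends on response to induction, which takes about 18 weeks in Stratum 1 and 12 weeks in Stratum 2. When the last required patient becomes evaluable, others are already under treatment, and Section 9.1 brings those who respond into the analysis.

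At stake is the primary decision in each stratum: whether reduced radiotherapy is good enough to pursue. Section 9.3.1 treats a PFS rate of 0.82 as unacceptable. A rule that accepts it one time in five, rather than one in twenty, is not the rule the study team designed.

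**Working it through.** **Inputs.** Stratum 1: null 0.82, alternative 0.93, N = 77, count 69 (Section 9.3.1). Stratum 2: null 0.87, alternative 0.95, N = 79, count 73 (Section 9.3.2). Patients not evaluated at three years count as failures (both sections), so loss to follow-up does not change N.

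**Formula.** With X ~ Binomial(N, p), type I error = P(X ≥ r) at the null rate, and power = P(X ≥ r) at the alternative.

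**The plan's own figures reproduce.**
- Stratum 1, N = 77, r = 69: type I error 0.0492, power 0.911.
- Stratum 2, N = 79, r = 73: type I error 0.0978, power 0.900.

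**How many extra patients to expect.** Assume that accrual stops when the target number has become evaluable. Those still in induction who will become evaluable number about (evaluable patients per year) × (weeks of delay) / 52.
- Stratum 1: Section 9.2.1 gives 11.1 evaluable patients per year. With 18 weeks of induction, 11.1 × 18/52 = 3.8. Counting to the latest permitted radiotherapy start (week 15 + 6 = week 21), 11.1 × 21/52 = 4.5.
- Stratum 2: Section 9.2.2 gives 10 to 18 per year. At 12 weeks, 10 × 12/52 = 2.3 to 18 × 12/52 = 4.2. At the latest start (week 9 + 6 = week 15), 10 × 15/52 = 2.9 to 18 × 15/52 = 5.2.

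So N of about 81 in Stratum 1, and about 81 to 84 in Stratum 2, would be ordinary outcomes.

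**Counts held fixed, N varied.**

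| Stratum 1, at least 69 | Type I error | Power |
|---|---|---|
| N = 77 | 0.049 | 0.911 |
| N = 78 | 0.085 | 0.955 |
| N = 80 | 0.202 | 0.990 |
| N = 81 | 0.281 | 0.996 |

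| Stratum 2, at least 73 | Type I error | Power |
|---|---|---|
| N = 79 | 0.098 | 0.900 |
| N = 80 | 0.168 | 0.953 |
| N = 82 | 0.365 | 0.992 |
| N = 84 | 0.590 | 0.999 |

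One extra patient takes either stratum above its intended level.

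**Count against p-value in Stratum 1.** With 69 of 80 progression free, the count rule declares success. The exact one-sided p-value is P(X ≥ 69 | 80, 0.82) = 0.20, which fails the 0.0492 criterion. Even at the design size, 69 of 77 has exact p = 0.04925, so a strict reading of the threshold would reject the plan's own boundary result; the threshold is evidently the rounded attained level.

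**Critical values re-derived at each N** (smallest count with exact type I error at most 0.05 in Stratum 1 and 0.10 in Stratum 2), as the largest number of failures allowed:

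| Stratum | N | Failures allowed |
|---|---|---|
| 1 | 70–76 | 7 |
| 1 | 77–83 | 8 |
| 1 | 84–87 | 9 |
| 2 | 70–78 | 5 |
| 2 | 79–88 | 6 |

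**The case against.** The best defence is that a test is already specified. Section 9.3.1 asks for a significant p-value without tying it to an N, and Section 9.3.2 names a one-sided test at 0.10. If an exact test at the realised N governs, type I error stays at or below nominal and only power moves. That stands as far as it goes. But the count is the rule actually written in each section, the two criteria disagree once N exceeds 77 in Stratum 1, and nothing ranks them. Stratum 2 has only a design level, with a count as its operative rule.

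A reader might infer that the stated error rates are miscalculated. They are not; both reproduce at the stated N.

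A reader might also average over a random N, supposing that accrual stops at exactly 125 and 123 eligible patients. That gives type I error and power of 0.19 and 0.74 in Stratum 1, and 0.28 and 0.72 in Stratum 2. The documents do not support that as the expected behaviour: no hard stop is stated, 125 is approximate, the total of 275 depends on the expected evaluable shares being realised, and Section 9.1 has accrual run until the cohort is reached. Loss of power from too few patients therefore arises only if accrual is capped.

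Nor should an overrun of 6 in Stratum 2 be taken as typical. It comes from the early rate of 80 patients in 27 months in Section 9.2.2; the section's projected evaluable accrual gives 2 to 5.

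**Conclusion.** The concern holds as a gap between the decision rule and the analysis set. The counts are calibrated for 77 and 79 patients, the set is uncapped, and a small overrun is the likely course. Taken literally, the counts then give type I error of 0.085 to 0.28 for N = 78 to 81 in Stratum 1, and 0.17 to 0.59 for N = 80 to 84 in Stratum 2.

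Two assumptions carry this: that accrual stops when the target number has become evaluable, at the plan's projected rates, and that the count rather than an exact test at the realised N decides. The first sets the likely size of the overrun; the sensitivity of the rule to each extra patient does not depend on it. The second is what the plan leaves open, and it should be settled before outcomes are known. The suspension triggers of 9 and 7 failures can stay: they apply while the cohort is still filling, and they lead to monitoring-board review rather than to a success decision.

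**What to change.** Choose one of two changes and write it into Sections 9.1, 9.3.1 and 9.3.2.

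(a) Define the primary analysis set as the first 77 (Stratum 1) and first 79 (Stratum 2) evaluable patients in enrolment order, with all treated patients as a supportive analysis. The counts and the stated error rates and power then stand. The cost is that a few treated patients fall outside the primary test.

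(b) Keep everyone, and state that the exact one-sided binomial test at the realised N governs, at 0.05 in Stratum 1 and 0.10 in Stratum 2, with the failure limits tabulated above. In Stratum 1 this replaces the 0.0492 threshold. The cost is some power: 0.87 to 0.91 for N = 78 to 83 in Stratum 1, and 0.85 to 0.90 for N = 79 to 88 in Stratum 2. If Stratum 2 ended at 78, power would be 0.805.

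Either needs a sentence or two per stratum, plus a small table for (b), and no additional patients.

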disease that would be required to address the primary study objective with statistical confidence even though considerable effort will be required to assure that no patient is lost to follow up within three years of initiating treatment. The study team is confident that this is possible.

In order for the reduced therapy approach to be considered to have sufficient merit for continued investigation, the null hypothesis must be rejected otherwise this approach will have to be reconsidered.

Due to the expected accrual rate, expected low failure rate and 3-year PFS endpoint, even one interim analysis for futility that would stop accrual early is not practical. If at any point in the trial, 7 patients are documented to have failed (progressed or been lost to follow up) before three years of follow up and fewer than 79 patients eligible for the primary analysis have begun treatment, accrual will be suspended until the COG DSMB has had the opportunity to review all data.

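### Stratum 1 states its success rule twice, and the two versions disagree at 69 of 77: the count rule accepts it, but "p-value < 0.0492" excludes it (exact p = 0.04925)

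*Combined protocol and SAP*

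**What the plan says.** Section 9.3.1 tests the Stratum 1 three-year PFS rate with a one-sample binomial design: "testing that the true, unknown 3-year PFS rate is at most 82% (null hypothesis: ≤ 0.82"), powered for 93%, with 77 evaluable patients. It gives the rejection rule as a count: "This design will reject the null hypothesis if at least 69 patients" are progression free after three years. It then reports what that rule achieves: "Due to the discrete distribution, the actual type I error rate is 0.0492", with power 0.911.

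The following paragraph restates the requirement for the approach to merit further study, this time as a significance threshold: "p -value < 0.0492. The null hypothesis must be rejected otherwise this approach will have to be reconsidered".

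The last paragraph of the section suspends accrual for DSMB review "if 9 patients are documented to have failed (progressed or lost to follow up) before three years of follow up" while fewer than 77 primary-analysis patients have begun treatment.

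Section 9.3.2 (Stratum 2 Germinoma) has the same structure without a p-value threshold. It says "This design will reject the null hypothesis if at least 73 patients" of 79 are progression free, and that for the approach "to have sufficient merit for continued investigation, the null hypothesis must be rejected otherwise this approach will have to be reconsidered".

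**The concern.** In a discrete one-sided test, the p-value at the boundary count equals the attained type I error of the rule. Using that attained error as a strict upper limit for the p-value therefore rules out the boundary count. Here 0.0492 belongs to 69 of 77, so requiring a p-value below 0.0492 rejects the result that the preceding paragraph accepts.

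With exactly 8 failures among 77 patients, one paragraph concludes that reduced therapy is acceptable and the next says it must be reconsidered. This is the decision rule for the stratum's primary PFS objective. Section 9.3.1 also counts every patient not evaluated for progression at three years as a failure, so a few missed assessments could bring a good result down to this boundary. Deciding which sentence governs once the count is known would be open to challenge as a post hoc choice.

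**Working it through.** **Inputs (Section 9.3.1):** n = 77; null rate 0.82; alternative 0.93; count rule of at least 69; attained type I error 0.0492; power 0.911; literal condition of a p-value below 0.0492; suspension at 9 failures. The ACNS0122 combined-cohort rate of 91.8% is in the same section.

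**Formula:** upper binomial tail P(X ≥ r | n, π) = Σ over x from r to n of C(n,x) π^x (1−π)^(n−x).

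**1. Reproduce the plan's figures.** P(X ≥ 69 | 77, 0.82) = 0.049248, which rounds to the stated 0.0492. P(X ≥ 69 | 77, 0.93) = 0.9111, as stated. The suspension trigger also fits a cut-off of 69: 77 − 69 + 1 = 9 is the first failure count at which 69 successes become impossible.

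**2. Apply the p-value sentence literally, using the exact one-sided tail.**

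| Progression free of 77 | Exact p (null 0.82) | Count rule | p below 0.0492 |
|---|---|---|---|
| 68 | 0.0934 | fail | fail |
| 69 | 0.049248 | pass | fail |
| 70 | 0.0230 | pass | pass |

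This is not a rounding effect. Unrounded, 0.049248 is not below 0.0492. Rounded, 0.0492 is not below 0.0492.

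**3. Operating characteristics of each reading.**

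| True 3-year PFS | P(X ≥ 69) | P(X ≥ 70) | P(X = 69) |
|---|---|---|---|
| 82% | 0.0492 | 0.0230 | 0.026 |
| 91.8% | 0.822 | 0.704 | 0.117 |
| 93% | 0.911 | 0.830 | 0.081 |

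The last column is the probability that the two rules give opposite answers. A cut-off of 70 does not have the stated error rates, so those rates belong to 69.

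**4. Sensitivity to the p-value method.** Section 9.3.1 does not name one. Under the null the mean is 77 × 0.82 = 63.14 and the SD is √(77 × 0.82 × 0.18) = 3.371. At 69/77:

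- Mid-p: 0.049248 − 0.026207/2 = 0.0361, pass.
- Normal without correction: z = (69 − 63.14)/3.371 = 1.738, p = 0.0411, pass.
- Normal with continuity correction: (68.5 − 63.14)/3.371, p = 0.0559, fail.

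Only the exact tail yields the printed 0.0492. At 68/77 the exact, mid-p and uncorrected normal values are 0.0934, 0.0713 and 0.0747, so none of them lowers the cut-off below 69.

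**5. Stratum 2 for comparison.** P(X ≥ 73 | 79, 0.87) = 0.0978 and P(X ≥ 73 | 79, 0.95) = 0.8999, in line with the stated 0.10 and 90%. The trigger 79 − 73 + 1 = 7 also agrees. With no p-value threshold in that text, there is no conflict.

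**The case against.** The strongest reply is that the intent is plain. The rejection rule is stated explicitly as a count, the figure 0.0492 is attached to it, and the later sentence goes straight on to require rejection of the null hypothesis, which points back to the rule just defined. On this reading the sentence contains a slip of "<" for "≤", nothing else in the plan supports 70, and applying 69 later would follow a pre-specified rule. The effect is also confined to one count, and the literal reading errs on the conservative side.

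The point about intent stands, and it makes the correction safe. It does not make the text consistent: the sentence with the strict threshold is the one that says what the design requires, and it gives the wrong answer at the boundary.

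A second reply is that the p-value method is unnamed and that mid-p or an uncorrected normal test would pass at 69/77. That is correct, but it means the verdict at 69 depends on an unspecified choice, which is a further reason for one explicit rule.

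A third reply concerns the remedy. Evaluability in Stratum 1 is known only after induction, so the analysed number may not be exactly 77, and a p-value criterion carries over to another n where a fixed count does not. Keeping 69 at n = 78 would give a type I error of 0.0854. This is a fair point, and the fix has to allow for it.

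**Conclusion.** The inconsistency is real. Section 9.3.1 gives two success criteria that disagree at 69 of 77 and nowhere else. The count rule is the design, and its sample size, type I error (0.0492), power (0.911) and suspension trigger are mutually consistent. The p-value sentence taken alone implies 70 of 77, with type I error 0.0230 and power 0.830; those are not properties of the design.

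The chance of landing on the disputed count is about 8% at the design alternative, 12% at the ACNS0122 rate and under 3% at the null. The conclusion assumes the exact one-sided binomial p-value, the only method tried that gives the printed 0.0492, and an analysed n of 77. It is a wording defect rather than a design error, but it sits in a primary decision rule and should be corrected.

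**What to change.** Remove the p-value threshold and make at least 69 of 77 progression free at three years the only Stratum 1 success criterion, matching how Stratum 2 uses 73 of 79. Report 0.0492 only as the attained type I error.

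If a p-value is kept, name the method and use a non-strict limit: exact one-sided binomial p-value against 0.82 no greater than its value at 69/77 (0.04925).

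In either case, say what happens if the analysed number is not 77, because a count applies to one n only. For n = 78, for example, the cut-off becomes at least 70 (exact p = 0.0445).

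The cost is one phrase plus that sentence, with no change to sample size, accrual or monitoring. It should be made before the three-year count is known.
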